8.2. Average Abdominal Pain Score (AAPS)

AAPS is the average of the APS score over each weekly assessment period (Wks 1, 2, 4, 6, 8). The Baseline value of AAPS will be derived as the average of the last (most recent) non-missing 7 days of morning and evening diary records within the Screening period prior to Day 1 of treatment. During the treatment period, summaries for a nominal week will be derived from the last 7 days within that period that contain a non-missing assessment. Summaries may be derived from fewer than 7 days (e.g., if the Wk 1 and Wk 2 Visits are less than 7 days apart). AAPS will be summarized for the Screening period and for each assessment week of treatment before morning dose (trough) assessments and 1.5 hours post-treatment first daily dose (peak) assessments, by treatment group and overall. Statistical comparisons of AAPS will be made between Screening and Wk 4 and Wk 8, trough and peak assessments, by treatment and overall. Change scores from Baseline for peak and trough at Wk 4 and Wk 8 will be derived. Treatment comparisons of the change scores will be analyzed using ANCOVA as for AAPS. The adjusted

treatment effect, 95% CI, and p-value will be presented. Overall changes from Baseline at Wk 4 and Wk 8 will be assessed using 1-sample t-tests as for AAPS. These analyses will be repeated for the Per Protocol population.

Peak and trough AAPS by treatment and visit will be plotted displaying treatment means and 95% CIs for the efficacy population only.

These analyses will be repeated where AAPS will be summarized for the Screening period and for each assessment week of treatment before evening dose (evening trough) assessments and 1.5 hours post first daily dose (peak) assessments, by treatment group and overall.

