3.3.2. Exploratory Endpoints

3.3.2.1. Abdominal Pain Score (APS) and Average Abdominal Pain Score (AAPS)

The APS is a PRO using a numerical rating scale (NRS) which is recorded in a subject diary. The 11-point NRS scale ranges from 0 (no abdominal pain) to 10 (worst possible abdominal pain) will be recorded by subjects in a diary as follows;

During Screening Period

APS is recorded twice daily for at least 7 consecutive days within the Screening period (Day -28 to Day -1), at the following times:

- 1. Early morning, approximately 06:00 08:00
- 2. Late evening, approximately 20:00 22:00

To establish a baseline for AAPS the following procedure will be adopted:

The last diary entry prior to treatment will be identified. The 7 consecutive days that terminate with this last data point constitute the Screening reference period. Baseline for AAPS is the mean of non-missing pain scores within the Screening reference period.

During Treatment Period

APS is recorded three times a day on each treatment Day (Day 1 to 56) at the following times:

- 1. Before the morning dose and before any other morning dose study procedures (i.e., at trough APD371 concentration)
- 2. Approximately 1.5 hours after the morning dose (i.e., at peak APD371 concentration)
- 3. Before the evening dose (i.e., at evening trough ADP371 concentration)

Note: Subjects will also be required to complete the diary before their first morning dose on Wk 0 (Day 1), and at the EOT Visit at Wk 8 in the early morning (06:00 - 08:00). If a subject discontinues the study, ET, the APS score will be assessed.

It should be noted that:

- The AAPS is derived for each assessment period (Wks 1, 2, 4, 6, 8). For Wks 4, 6, and 8 scores are collected from the previous 7 days of diary entries prior to the visit day. 'Peak AAPS' is the mean of non-missing APS recorded at the time of peak concentration for those 7 days. Likewise, 'Trough APS' is the mean of non-missing APS recorded at the time of trough concentration for those 7 days. Similarly, 'Evening Trough APS' is the mean of non-missing APS recorded at the time of evening trough concentration for those 7 days. Wk 1 and Wk 2 peak, trough, evening trough, and overall AAPS are derived in a similar manner but note that:
 - For Wk 1, as Day 1 is neither peak nor trough, and APS scores cannot be accurately identified as pre-dose or post-dose, scores on Day 1 are disregarded. Hence, AAPS scores may be obtained from fewer than 7 days.

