4.7.3. Missing Data

As described in Section 8.3, in responder analyses, subjects with missing data will be classified as non-responders. Otherwise, there will be no imputation of missing data.

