8.1. Abdominal Pain Score (APS)

For each subject, APS score measured at peak will be averaged over the entire treatment period. Likewise, the APS score measured at trough will be averaged for each subject. The difference (peak - trough) will be calculated, per subject, as mean (peak) - mean (trough).

Mean peak, trough, and peak - trough will be summarized by treatment and overall. The peak - trough differences will be analyzed between treatments using an analysis of covariance (ANCOVA) model with treatment as a factor and Baseline score as a covariate. The 95% CI for the adjusted treatment difference will be presented together with the p-value. For the pooled data, a 1-sample t-test will be conducted testing against the hypothesis of zero difference between peak and trough. The 95% CI for the overall difference between peak and trough assessments will be presented.

Additionally, the APS score measured prior to evening dose (evening trough) will be averaged for each subject. The difference (peak - evening trough) will be calculated, per subject, as mean (peak) - mean (evening trough). The analysis will be repeated using mean peak, evening trough, and peak - evening trough and will be summarized by treatment and overall.

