8.3. Pain Relief Responders

For each of Wks 1, 2, 4, 6, 8 a subject with a missing AAPS will be coded to non-responder. The number and proportion of responders for Wks 1 to 8 and at EOT will be tabulated by treatment group and overall. The difference in proportions of peak, trough, evening trough, and average daily pain weekly responders between the treatment groups at Wk 8 and EOT will be tested by Fisher's exact test and the p-value presented.

These analyses will be repeated for the Per Protocol population.

The percentage of peak, trough, evening trough, and average daily pain weekly responders will be plotted by treatment and visit for the Efficacy population only.

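### SAP 8.2 tests AAPS change at Wk 4 and Wk 8 separately on observed data only; if dropout follows poor relief, the pooled improvement is overstated, so a repeated-measures model should be added alongside

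*SAP*

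**What the plan says.** SAP 8.2 sets up the tests in three steps. First, "Change scores from Baseline for peak and trough at Wk 4 and Wk 8 will be derived". Second, for the dose comparison, "Treatment comparisons of the change scores will be analyzed using ANCOVA as for AAPS". Third, for the pooled result, "Overall changes from Baseline at Wk 4 and Wk 8 will be assessed using 1-sample t-tests as for AAPS". The phrase about AAPS in the last two sentences points back to the section it stands in. I read it as referring to SAP 8.1, where the ANCOVA has dose and Baseline score as its only terms.

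On missing data, SAP 4.7.3 makes an exception for the responder analyses and then says: "Otherwise, there will be no imputation of missing data". The exception is in SAP 8.3: "For each of Wks 1, 2, 4, 6, 8 a subject with a missing AAPS will be coded to non-responder".

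SAP 3.3.2.1 derives AAPS at five on-treatment points, Wks 1, 2, 4, 6 and 8. All five are summarized, but only Wk 4 and Wk 8 enter the tests of change. The 8.2 analyses are repeated only on the Per Protocol population, which is a subset.

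SAP 8.1 does keep partial records ("For each subject, APS score measured at peak will be averaged over the entire treatment period", and likewise at trough), but it tests peak minus trough, not change from Baseline.

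**The concern.** A subject who stops treatment and diary entries part-way has a Wk 1 and perhaps a Wk 2 or Wk 4 AAPS, yet drops out of the Wk 8 test. If subjects with less relief are more likely to stop, those left at Wk 8 are the ones doing better, and their mean change is too favourable. The pooled test has no control arm in which that selection could cancel.

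The responder analysis keeps the same subject as a failure, so the two main pain results can rest on different subjects.

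Protocol 8.2 and SAP 4.1 say the study should quantify the extent of pain relief, and the pooled change from Baseline is the most direct measure of that. Selective loss is possible: the trial is open-label, subjects may withdraw at any time (Protocol 5.14), and treated subjects who discontinue are in general not replaced (Protocol 5.14.2). The SAP amendment also added responder tables on observed data. Those would merely repeat the existing tables if no AAPS were missing, so some missing values are likely.

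**Working it through.** The documents state no effect size, SD, correlation or dropout rate, so there is no figure of theirs to reproduce. The size of the problem has to be simulated.

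**From the documents:** 16 subjects, 8 per dose (SAP 3.1); AAPS at Wks 1, 2, 4, 6 and 8 (SAP 3.3.2.1); observed data only (SAP 4.7.3).

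**Assumed:**
- mean change -1.0, -1.4, -1.8, -2.0, -2.0 at the five weeks
- SD 2.0 at each week, equal correlation of 0.5 or 0.8 between weeks
- everyone observed at Wk 1, no return after leaving
- total dropout by Wk 8 of 12.5%, 25% or 37.5%

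**Dropout at week j:** logit P = a + 1.5 × (Y − mean)/SD, with a set to give the target total. Y is the change at the previous recorded week (missing at random, MAR) or at the current unrecorded week (missing not at random, MNAR). For unrelated dropout (MCAR), logit P = a.

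**Bias** = estimated Wk 8 change − (−2.0); negative means improvement is overstated. The model is a random-intercept (compound-symmetry) likelihood fit with a mean for each week. Dose and Baseline terms are left out, since the target here is the pooled change.

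Large-sample bias, correlation 0.5 / 0.8:

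| Dropout | Total | Observed-case mean | Model |
|---|---|---|---|
| MCAR | 25% | -0.01 / 0.00 | +0.01 / -0.01 |
| MAR | 12.5% | -0.17 / -0.26 | +0.01 / 0.00 |
| MAR | 25% | -0.33 / -0.50 | -0.01 / -0.01 |
| MAR | 37.5% | -0.49 / -0.74 | -0.01 / 0.00 |
| MNAR | 12.5% | -0.21 / -0.27 | -0.11 / -0.06 |
| MNAR | 25% | -0.41 / -0.53 | -0.22 / -0.11 |
| MNAR | 37.5% | -0.61 / -0.79 | -0.31 / -0.16 |

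**At n = 16 and 25% dropout** (3,000 replicates, about 12 subjects left at Wk 8; the roughly 1% of replicates with fewer than 8 left were set aside), bias with the SD of the estimate in brackets:

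| Dropout | Correlation | Observed-case | Model |
|---|---|---|---|
| MAR | 0.5 | -0.34 (0.56) | -0.01 (0.56) |
| MAR | 0.8 | -0.50 (0.53) | -0.02 (0.52) |
| MNAR | 0.5 | -0.39 (0.54) | -0.19 (0.53) |
| MNAR | 0.8 | -0.54 (0.52) | -0.12 (0.50) |

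A separate simulation with the same SD, size, dropout rate and correlation range gave observed-case bias of -0.28 to -0.44 under MAR (model about 0) and -0.34 to -0.45 under MNAR (model -0.07 to -0.17).

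**Scaling.** Dropout depends on the deviation from the mean in SD units, so the bias does not depend on the assumed true change and is proportional to SD. At 25% MAR it is 0.33/2 = 0.16 to 0.50/2 = 0.25 SD.

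**Between doses.** With equal selective dropout the two biases largely cancel. With MAR dropout of 12.5% in one dose and 37.5% in the other, the difference shifts by 0.488 − 0.174 = 0.31 (correlation 0.5) or 0.736 − 0.258 = 0.48 (correlation 0.8), in favour of the dose that loses more subjects.

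**Covariance.** Five weeks need 5 × 6/2 = 15 unstructured parameters, too many for about 16 subjects. Under MAR at n = 16 the unstructured fit has SD 0.55 to 0.61, against 0.52 to 0.56 for compound symmetry.

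**The case against.** The strongest case against is that nothing shows dropout to be related to pain.

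- The documents give no dropout rate, and the discontinuation reasons in SAP 5.2 have no category for lack of efficacy.
- Protocol 4.9.2 permits rescue and stable analgesics, so leaving is not the only course for a subject in pain.
- Blood-pressure events are not pain events. The visible text also provides for dose reduction (SAP 3.1) and for interruption with re-start (Protocol 4.6.1), so withdrawal on those grounds does not by itself make dropout pain-related.

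All of this stands, and it makes the overstatement conditional.

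The near-zero bias of the model under MAR is also partly built in, because the simulated dropout meets the model's own assumption and the simulated correlation is compound-symmetric. If correlation instead decays over time, a further check at SD 2 and 25% MAR dropout left +0.06 to +0.10 points under the compound-symmetry model. Under MNAR the model removes about half to four-fifths of the bias.

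Partial safeguards exist. Responders are reported with missing counted as failure and on observed data, non-missing counts accompany each summary (SAP 4), and AAPS is summarized at every assessment week. The trial is exploratory, with no primary endpoint and no formal testing strategy, and SAP 8 allows inference to be dropped if numbers are very low. These limit the importance of the point, but none of them corrects the mean change.

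The Wk 4 test is less clear-cut. SAP 3.3.2.1 uses the 7 days before the visit, while SAP 8.2 uses the last 7 days with data within the period. Under the second wording a subject who stopped in Wk 3 might still have a Wk 4 value. The Wk 8 test is the cleaner case.

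A reader might also infer that this mean change will size and dose the next study. The documents do not say so: Protocol 3.3 names safety, tolerability and PK data as the guide to dose and regimen.

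**Conclusion.** The gap is real: AAPS change is tested one week at a time on whoever has data, and the Wk 1, 2 and 6 scores inform no test. The consequence is conditional. If dropout follows poor relief, the pooled one-sample t-test at Wk 8 overstates improvement by about 0.3 to 0.5 points, assuming SD 2, n = 16, correlation 0.5 to 0.8 and 25% dropout. Under MAR at n = 16 that is 0.34/0.56 = 0.6 to 0.50/0.53 = 0.9 of the standard deviation of the estimate. With unrelated dropout, or none, it is nil.

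Four stronger readings are not supported:

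- That improvement is overstated as a matter of fact. This needs pain-related dropout, which the documents neither show nor rule out.
- That the dose comparison is inflated. There the bias can cancel or go either way, and ANCOVA tolerates dropout that depends only on dose and Baseline pain.
- That a repeated-measures model cures the problem. It removes the bias under MAR with a suitable covariance and reduces it otherwise. It cannot recover subjects whom SAP 4.5 excludes from the Efficacy population for lack of 7 on-treatment diary days by Wk 4.
- That the planned intervals are materially too wide. In the MAR runs the SD of the estimate is almost the same for both methods (0.53 to 0.56 against 0.52 to 0.56).

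The argument for the change is bias, not precision. It is a worthwhile addition and does not invalidate the specified tests.

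**What to change.** In SAP 8.2, add one repeated-measures mixed model per measure (peak, trough, evening trough, daily average):

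- response: AAPS change at Wks 1, 2, 4, 6 and 8
- terms: dose, week, dose-by-week, Baseline AAPS
- compound-symmetry covariance with Kenward-Roger degrees of freedom
- report Wk 4 and Wk 8 changes by dose, pooled, and between doses, with 95% CIs

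Present it alongside the specified ANCOVA and t-tests, not in place of them. Label it post hoc, since this SAP version was written after database lock (14 September 2018, relocked 19 November 2018) on open-label data.

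With it, report the number of subjects contributing to each week's AAPS and the reasons for leaving by week. Add one MNAR sensitivity analysis, for example a fixed worsening added to leavers' predicted scores over a stated range. State that subjects excluded by the 7-day rule remain outside the model.

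The cost is SAP wording, one SAS PROC MIXED call per measure and a few extra tables, with no new data. The price in assumptions is reliance on MAR and on a simple covariance, which the sensitivity analysis and the retained observed-case results let the reader judge.

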8.3. Pain Relief Responders

For each of Wks 1, 2, 4, 6, 8 a subject with a missing AAPS will be coded to non-responder. The number and proportion of responders for Wks 1 to 8 and at EOT will be tabulated by treatment group and overall. The difference in proportions of peak, trough, evening trough, and average daily pain weekly responders between the treatment groups at Wk 8 and EOT will be tested by Fisher's exact test and the p-value presented.

These analyses will be repeated for the Per Protocol population.

The percentage of peak, trough, evening trough, and average daily pain weekly responders will be plotted by treatment and visit for the Efficacy population only.

8.6. C-reactive protein (CRP)

CRP will be summarized by visit (Baseline, Wk 4, Wk 8). Within subject changes from Baseline at Wk 4 and Wk 8 will be analyzed by treatment and overall using dependent means t-tests. Mean change, 95% CIs and p-values will be presented. Changes from Baseline at Wk 4 and Wk 8/EOT will be analyzed using an ANCOVA model with treatment as a factor and Baseline value as a covariate. Adjusted treatment effects with p-values and 95% CIs will be presented. CRP by treatment and visit will be plotted for the Efficacy population displaying treatment means and 95% CIs. A scatterplot will be produced of change from Baseline in CRP and change from Baseline in peak AAPS at Wk 8 for all subjects (irrespective of treatment) in the Efficacy population. A regression line will be fitted.

8.7. Fecal Calprotectin

Fecal calprotectin will be summarized by visit (Baseline, Wk 4, Wk 8). Within subject changes from Baseline at Wk 4 and Wk 8 will be analyzed by treatment and overall using dependent means t-tests. Mean change, 95% CIs and p-values will be presented. Changes from Baseline at Wk 4 and Wk 8 EOT will be analyzed using an ANCOVA model with treatment as a factor and Baseline value as a covariate. Adjusted treatment effects with p-values and 95% CIs will be presented. Fecal calprotectin by treatment and visit will be plotted for the efficacy population displaying treatment means and 95% CIs. A scatterplot will be produced of change from Baseline in fecal calprotectin and change from Baseline in peak AAPS at Wk 8 for all subjects (irrespective of treatment) in the Efficacy population. A regression line will be fitted.

8.9. Number of Pain-Free Days

The number of pain-free days per week will be summarized by visit (Screening, Wks 1 to 8). The Screening score will be derived from the screening reference period as defined in Section 3.3.2.1. Because few subjects had pain-free days either at Screening or post-baseline, no inferential analyses will be conducted.

8.10. Use of Rescue Medication

The number of subjects using rescue medication during the Screening period and at any time during active treatment will be tabulated by treatment group and overall by shift table. Because of the paucity of data with respect to changes, no inferential analyses will be conducted.

9. SAFETY ANALYSES

Safety and tolerability will be assessed by a review of all safety parameters including AEs, laboratory safety parameters, vital signs, and ECG. Only summary tabulations (N, n, mean [or median], SD, mean [or median] change/percent change, percentage) and 95% CIs for between-group differences will be obtained. AEs will be presented as summary tabulations and listed.

9.1. Adverse Events

AEs will be coded using MedDRA (Version 21.0) and tabulated, including categorical information of interest such as onset and resolution times, time of onset relative to dose, severity at onset, maximum severity, causal relationship to study medication, and action taken. AEs will be regarded as 'pre-treatment' if they occur between Screening and the time of administration of the first dose of APD371 and will be recorded as medical history. All other AEs that occur after the first dose of study medication will be considered to be 'treatment'.

Treatment-emergent AEs (TEAE) will be listed by subject and by treatment. They will be summarized per treatment and expressed in terms of maximum severity and relationship to study medication. The incidence of TEAEs classified according to system organ class will be summarized by treatment group. TEAEs will also be summarized by maximum intensity (assessed according to the Common Terminology Criteria for Adverse Events v4.032 definitions) and relatedness to study medication.

Summaries of the number (%) of subjects in each treatment group with at least one TEAE, classified according to MedDRA system organ class (SOC) and preferred term (PT), will also be provided for:

- Drug-related TEAE
- TEAEs leading to permanent discontinuation of study medication (study medication discontinued or withdrawal from study).
- Serious adverse events (SAEs)

SAEs will be listed by subject and by treatment. If there are no SAEs at the end of the study, the tables or listings will state that there are no SAEs in the study.

9.2. Physical Examinations

Physical examination results (abnormalities only) will be listed and summarized by treatment group.

9.2.1. Vital Signs

Supine vital sign measurements (blood pressure, pulse rate, respiratory rate, and oral body temperature) are taken at the following timepoints:

- Initial and final Screenings
- Wk 0 (Day 1) prior to and 0.5, 1, 2, 4, 6 and 8 hours after the first daily dose (prior to second daily dose) and 9 and 10 hours (1 and 2 hours after the second daily dose).
- Once a day on Wk 0 (Day 2), at the end of Wk 1 (Day 8), 2, 4, 6 and 8 and at the Followup Visit at Wk 10
- Wk 8 (Day -1) prior to and 0.5, 1, 2, 4, 6 and 8 hours after the first daily dose (prior to second daily dose) and 9 and 10 hours (1 and 2 hours after the second daily dose).

All vital sign measurements will be listed by treatment. Assessments and changes from Baseline will be summarized for blood pressure (BP), pulse rate, respiratory rate, and temperature by treatment at all timepoints. Baseline is defined as the last pre-treatment measurement.

9.2.2. Active-Standing Test

The Active Standing Test measures BP and heart rate (HR) before and after changing the position from supine to standing. The test will be performed by the bedside by measuring BP and HR after the subject has been resting in the supine position for 5 minutes and then after 1 and 3 minutes of standing. The test will be performed at the following timepoints:

- Day 1: pre-dose, 2, 4, 6, 8 and 10 hours after first dose
- Day 2: 2, 4 and 6 hours after the first dose
- Wks 1, 2, 4, 6 and 8: 2 hours after the first dose

The active-standing test will be performed if subjects discontinue the study (ET).

At each time point, differences between active-standing and supine assessments will be derived for SBP, DBP, and HR:

- Active Standing (1 minute) Supine
- Active Standing (3 minute) Supine

These derived variables and their changes from baseline will be summarized by treatment at all timepoints throughout the trial.

Individual subject profiles will be produced presenting the following data points on a single plot per subject at all timepoints:

• Supine DBP (mmHg)

Statistical Analysis Plan APD371-004

- Active Standing DBP (1 minute) (mmHg)
- Active Standing DBP (3 minutes) (mmHg)
- Supine SBP (mmHg)
- Active Standing SBP (1 minute) (mmHg)
- Active Standing SBP (3 minutes) (mmHg)
- Supine HR (bpm)
- Active Standing HR (1 minute) (bpm)
- Active Standing HR (3 minutes) (bpm)

In addition, a summary of orthostatic hypotension and postural tachycardia will be presented. Specifically, the number of subjects (%) that have orthostatic hypotension (defined as a decrease in SBP of 20 mmHg or greater relative to supine or a decrease in DBP of 10 mmHg or greater relative to supine), postural tachycardia (defined as an increase in heart rate of 30 bpm or greater relative to supine or a maximum of 120 bpm), or both will be presented by treatment at all timepoints and summarized by treatment group and overall.

